5.0 Inclusion and Exclusion Criteria/ Study Population

Inclusion Criteria

To be eligible for this study, the patient must be all of the following criteria:

Ages Eligible for Study: 18 years and older (adult, Senior). the condition is rare in children as compared to adults.

Sexes Eligible for Study: All

1. Completed cancer treatment (e.g. surgery, chemotherapy and radiation) > 6 months. Patients with current endocrine therapy will be included for the study.
2. Have been diagnosed with noninvasive or invasive (Stage 1, 2, or 3A) lung cancer, head and neck cancer, breast cancer or prostate cancer.
3. Smoke 5 or more cigarettes per day and have a carbon monoxide (CO) level > 5 ppm indicative of recent smoking.
4. Not have received substance abuse treatment within the previous 30 days.
5. Meet criteria for low to moderate nicotine dependence as determined by the FTND ≥ 1 .
6. Be willing to provide informed consent.
7. Be able to comply with protocol requirements and likely to complete all study procedures.
8. Is willing to consider trying to quit smoking.
9. Have no active cardiac, neurologic, or psychiatric illness.
10. 1 week -10 years post diagnosis of cancer at the time enrollment.

Exclusion Criteria

To be eligible for this study, the patient CANNOT meet any of the following criteria:

1. Current dependence, defined by DSM-V criteria, on any psychoactive substances other than nicotine or caffeine.
2. Contraindication to rTMS (history of neurological disorder or seizure, increased intracranial pressure, brain surgery, or head trauma with loss of consciousness for > 15 minutes, implanted electronic device, metal in the head, or pregnancy).
3. History of autoimmune, endocrine, viral, or vascular disorder affecting the brain.
4. History of neurological disorder that would lead to local or diffuse brain lesions or significant physical impairment.

6.0 Number of Subjects

The study will recruit 20 cancer patients who smoke 5 or more cigarettes per day.

7.0 Setting

1. The TMS treatment will be completed at Brain Stimulation Division in the Department of Psychiatry.
2. Screening and follow-up will be completed at Hollings Cancer Center (HCC).

Study Site

A single study site is at the Medical University of South Carolina.

8.0 Recruitment Methods

1. Research staff member will recruit participants from Health Tobacco Treatment Program and HCC via flyers, internet and emails at MUSC.
2. **Methods** (1) We will recruit participants from Health Tobacco Treatment Program and HCC at MUSC (2) Initial assessment: An informed consent procedure will be completed prior to

conducting any research procedures. Study personnel will review the consent with the participants and assess participant's understanding of the study. Participants not able to understand the consent after help from the study personnel, and those either excluded or unwilling to participate after the informed consent procedure, will be provided with an appropriate referral for smoking cessation if they are interested. (3) After the informed consent procedure, participants will be assessed for study inclusion/exclusion criteria. Each potential subject will be asked about their current height and weight, past medical history focusing on chronic (and current) medical problems, seizure history, medications, psychiatric disorders, and substance use. The research procedures, risks and benefits will be explained.

9.0 Consent Process

Informed consent will be completed prior to conducting any research procedures. The patient will be given sufficient time to read the informed consent and the opportunity to ask questions. Study personnel will review the consent with the participants in a private setting and assess participant's understanding of the study. Patients will be informed that the participation is voluntary and that they may withdraw consent to participate at any time, they will be informed that choosing not participate will not affect the care that patient will receive for the treatment for his/her cancer. Participants not able to understand the consent after help from the study personnel, and those either excluded or unwilling to participate after the informed consent procedure, will be provided with an appropriate referral for smoking cessation if they are interested. After having obtained the consent, a copy of the informed consent form will be given to the patient.

10.0 Study Design / Methods

10.1 General Design of the Study

This is a randomized, double-blinded design of active rTMS and sham rTMS. The pilot will include a total of 20 nicotine-dependent patients with cancer. Subjects will be randomized to either sham rTMS or real rTMS over the left DLPFC. At the end of 7-day study, everyone can be referred to the Hollings Cancer Center (HCC) Tobacco Treatment Program for active treatment.

10.2 Baseline Evaluation

After the informed consent is obtained, participants will be assessed for study inclusion/exclusion criteria.

(1) Demographic Data: Basic demographic information including age, gender, race, and medical history will be collected. (2) Mini International Neuropsychiatric Interview (MINI) (32): This is a well-standardized structured instrument used to provide quick and accurate DSM-IV psychiatric diagnoses. The MINI will be used to confirm the inclusionary/exclusionary diagnoses in the participants. (3) Tobacco Use History: Detailed history of current and past tobacco use will be obtained, including cigarette smoking. The questions addressed will include the amount, frequency, duration of smoking, preferred brand, reasons for smoking, smokeless tobacco, family history, etc. (4) Fagerstrom Test for Nicotine Dependence (FTND)(33): This is a self-rating questionnaire for nicotine dependence. (5) Questionnaire of Smoking Urges- Brief (QSU-B) (34): This is a 10-item self-rating questionnaire for assessment of craving. (6) Minnesota Withdrawal Scale - Revised (MNWS-R) (35): MNWS-R is a DSM-IV based instrument to assess symptoms of nicotine withdrawal. (7) Biomarkers: We will also use carbon monoxide (CO) level in the expired air by a standard CO breathalyzer at each visit. (8) Tobacco diary: This is a daily diary of all tobacco products consumed in the period between visits,

including cigarettes. Participants will maintain a daily tobacco diary, which will be collected at each visit.

10.3. TMS Procedures

(1). All TMS procedures will be performed by a highly trained faculty or staff member of the Brain Stimulation Laboratory at MUSC under the supervision of a licensed M.D. with specialized training in TMS delivery. (2). Treatment parameters and grouping – The time in the chair and the number of pulses on the head will be the same for all subjects. Active or sham TMS will be the only difference. The sham group only receives sham at all treatments. Stimulation frequency for all active subjects: 10 Hertz – Pulse train duration (on time) 5 seconds, Inter-train interval (off time) 10 seconds (15 second cycle time), Power (intensity) level 100% rMT, Total 60 trains, 15 minutes, Total pulses 3000 per day, $3000 \times 5 = 15000$ pulses for 5 sessions. If patients can not complete 5 sessions, they can complete 5 sessions within 7-day quit attempt (3). Subject Preparation for TMS delivery - The subject will be asked to remove and store any glasses or earrings, and to remove wallets from their pockets if they contain magnetic media (e.g., credit cards). They will be asked to empty their bladder to avoid treatment interruption. Ear protection will be provided. (4). Resting Motor Threshold (rMT): At entry, we will determine each subject's rMT and all rTMS dosing will be given relative to this value. The coil will be positioned over the area of the skull roughly corresponding to the motor cortex and then systematically moved and adjusted until each pulse results in isolated movement of the right thumb. Once we completed "threshold hunting", we will use a modified PEST algorithm attached EMG to determine rMT. (5). Localizing the TMS Coil over DLPFC: At a visit after providing informed consent, participants will be fitted with a white lycra swim cap. This cap will be worn during all TMS sessions in order to insure proper placement of the TMS coil across visits. Localization of the stimulation site in the prefrontal cortex will be performed using Bean Method developed by our team (36). (6). Treatment administration: The Neuronetics TMS will be used for the study. (7). Active Sham rTMS: Successful patient and operator masking is key to the success of this trial. In one of our previous studies, we have successfully developed an active sham system (37). To further assess the adequacy of the mask, TMS administrators, clinical raters, and patients will complete "best guess" questionnaires, assessing their best guess as to treatment condition, and their level of confidence in this guess.

10.4. The 7 days of a quit attempt: Participants will be asked to start a quit attempt after the first TMS session.

During the abstinence attempts, subjects will be told that you "go as long as you can without smoking". We will compare the numbers of cigarettes smoked and days of abstinence between active rTMS week and sham rTMS week.

10.5 Study Calendar

Timepoints	Baseline	TMS 1	TMS 2	TMS 3	TMS 4	TMS 5	Follow-up
Assessments							
Informed Consent	X						
Demographic	X						
Medical history	X						
Tobacco Use History	X						
Fagerstrom Test for Nicotine Dependence (FTND)	X						
Questionnaire of Smoking Urges- Brief (QSU-B)	X						

Minnesota Withdrawal Scale - Revised (MNWS-R)	X						
carbon monoxide (CO)	X						
Tobacco diary	X						
Primary Outcome – number of abstinence days	X	X	X	X	X	X	
Secondary Outcome – cigarette per day	X	X	X	X	X	X	
Visual analog scale of craving for cigarette	X	Pre and post X					
Adverse Events		X	X	X	X	X	
Best guess		X				X	
Phone call							X

11.0 Specimen Collection and Banking

Not applicable.

12.0 Data Management

12.1. Data collection

Data analyses will include the use of descriptive statistics for feasibility metrics and outcome measures. Graphical displays will be used to illustrate the effect of rTMS vs. sham TMS on the outcomes over time. General linear mixed models, ideal for modeling repeated longitudinal outcome data, will be used to estimate the potential treatment benefit of rTMS on numbers of cigarettes smoked per day. Poisson (or negative binomial) regression models will be used to estimate the potential treatment benefit of rTMS on numbers of days abstinent from cigarette smoking during their 7-days following their quit attempt. The regression models will allow us to estimate rTMS treatment benefit along with 95% confidence intervals. All analyses will be conducted in collaboration with the SCTR BERD biostatisticians.

The data from follow-up will be used to measure the durability of one week rTMS treatments. We hypothesized that the number of quit day would predict a long-term effect for smoking cessation.

Electronic and hard copy CRF's will be provided for the recording of data. With the exception of hard copy case report forms utilized for expedited reporting requirements, such as the reporting of SAE's, the remainder of patient data will be collected and submitted via electronic CRFs. All data should be substantiated by clinical source documents organized within a patient research record. ICH Good Clinical Practices are to be followed.

Electronic data for on study and follow-up patient data is submitted via REDCap. REDCap is managed from the Medical University of South Carolina as a consortium partner under their CTSA. REDCap CRF is a secure, Web-based application designed to capture and manage research study data.

The system has been reviewed for 21CFR Part 11 compliance and has been deemed "21CFR 11 Capable." Users of the REDCap system are limited to members of the IRB approved research team

who are delegated data management responsibilities, typically the study coordinator and data manager.

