4.2 Secondary efficacy endpoints

Total number of smoke-free days during a 7-day quit attempt. Self-reported abstinence during the 7-day quit attempt will be assessed via timeline. The maximum number of consecutive days of abstinence will be recorded. Participants who does not report at least one 24-hour period of abstinence will be recorded as "0" days abstinent.

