12.2 Data analysis

General considerations: All data will be analyzed in consultation ([name]) with the electronic system called REDCap (Research Electronic Data Capture). Statistical analyses will be performed using SPSS 22.0 (IBM Inc.). Baseline demographic and baseline characteristics, together with safety analyses will be performed on all enrolled subjects. Baseline values are defined as the measures on screening visit. The standard summary statistics for continuous variables are: mean, standard deviation, median, minimum and maximum. The standard summary statistics for categorical variables are: count and percentage. All statistical tests will be two-sided. For comparison of means (continuous variables), the two-sample t-test or the Wilcoxon rank sum test will be used as appropriate. For comparison of proportions (discrete data), the Chi-squared test will be used as appropriate. All test performed at significance $\alpha = 0.05$.

To assess a feasibility of the rTMS for smoking cessation in cancer patients: The numbers of subjects who were randomized and who entered and completed each visit of the study will be provided, as well as the reasons for all post-randomization discontinuations, grouped by treatment and by major reason. The discontinued subjects, protocol deviations, and subjects excluded will be provided as well.

To obtain the secondary estimates: The abstinence days, and cigarette consumption and cue-elicited craving will be compared between the active TMS and sham groups with a t-test or a repeated measures analysis of covariance model. Baseline daily number of cigarettes smoked, sex and center will be used as covariates.

To analyze the exploratory measures: cue-induced craving (QSU – Brief) and visual analog scale for craving will be measured pre and post each rTMS session. Other assessment, Carbon Monoxide, FTND, and MNWS-R will be compared between two groups.

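### Smoke-free days (0–7) has two unranked sets of analysis methods and no stated standard-error type, and one permitted choice, unscaled Poisson, can give a wrong 95% interval

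*Combined protocol and SAP*

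**What the plan says.** Section 4.2 defines the outcome as "Total number of smoke-free days during a 7-day quit attempt": one whole number from 0 to 7 per patient. It adds that "The maximum number of consecutive days of abstinence will be recorded", without saying what that second measure is for.

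The analysis of abstinent days appears in two places.

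- Section 12.1: "Poisson (or negative binomial) regression models will be used to estimate the potential treatment benefit of rTMS on numbers of days abstinent". It continues: "The regression models will allow us to estimate rTMS treatment benefit along with 95% confidence intervals". It gives no rule for choosing Poisson or negative binomial, no covariates and no standard-error type (model-based, robust or dispersion-scaled).
- Section 12.2: abstinence days, cigarette consumption and craving "will be compared between the active TMS and sham groups with a t-test or a repeated measures analysis of covariance model", and "Baseline daily number of cigarettes smoked, sex and center will be used as covariates". The general rule for means in the same section is that "the two-sample t-test or the Wilcoxon rank sum test will be used as appropriate", with no criterion. Tests are two-sided at 0.05.

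No section says which of these is the main analysis.

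**The concern.** Two sets of methods are assigned to one outcome, and they do not estimate the same quantity. The count models give a ratio of mean days; the t-test gives a difference in mean days. The repeated-measures model may be meant only for outcomes measured repeatedly, since the 7-day total is a single value per patient. On that reading the conflict is still count model against t-test.

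The choice matters because the methods handle variability differently. A t-test estimates the variance from the data. Poisson regression with model-based standard errors sets the variance equal to the mean. If patients split into early relapsers and full-week abstainers, the variance can exceed the mean and the Poisson interval is too narrow. If days are nearly independent within a patient, the cap at 7 pulls the variance below the mean and the interval is too wide. The first error is the harmful one, because it overstates the evidence; the second loses precision.

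Section 1.2 asks for preliminary estimates of efficacy, and 12.1 says the regression models supply them with their intervals. The stated precision of those estimates is what is at stake.

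**Working it through.** The plan gives no standard deviation, abstinence rate, effect size or power for this outcome, so there is no figure to reproduce. The check asks how each permitted method behaves when there is no treatment effect.

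**Inputs**

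- 20 patients in two arms (section 10.1). The allocation ratio is not stated; 10 per arm is assumed.
- Outcome 0–7 (section 4.2); two-sided 0.05 (section 12.2).
- Section 2.4 puts first-week relapse at 50–75%, so 25–50% abstinent all 7 days is taken as the working range. That figure describes smokers in general, not cancer patients.
- The shape of the distribution is assumed, and several are tried.

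**Step 1: when does variance equal the mean?** With mean m, the same abstinence probability each day and within-patient correlation ρ between days,

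variance/mean = (1 − m/7)(1 + 6ρ).

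This equals 1 only at ρ = 0.17 for m = 3.5, 0.30 for m = 4.5 and 0.50 for m = 5.25. Stronger clustering gives over-dispersion, weaker gives under-dispersion.

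**Step 2: over-dispersion without that assumption.** Let each patient relapse with constant daily chance q and not return to abstinence.

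- 25% abstinent all week: (1 − q)^7 = 0.25, so q = 0.180. Mean 3.42, SD 2.64, variance/mean = 2.64²/3.42 = 2.04.
- 50% abstinent all week: q = 0.094. Mean 4.80, SD 2.60, variance/mean = 2.60²/4.80 = 1.41.

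**Step 3: from dispersion to error rate.** The model-based Poisson standard error is 1/√(variance/mean) times the true one. The false-positive rate is therefore approximately 2[1 − Φ(1.96/√(variance/mean))].

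- 2.04: 1.96/1.428 = 1.372, giving 17.0%.
- 1.41: 1.96/1.187 = 1.651, giving 9.9%.
- 2.30: 1.96/1.517 = 1.292, giving 19.6%.
- 0.55: 1.96/0.742 = 2.643, giving 0.8%.

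**Step 4: simulation under no effect**, 40,000 trials per row (20,000 for negative binomial). In the mixtures, the stated share has 7 days and the rest are spread evenly over the range shown.

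| Assumed distribution | Variance/mean | Plain Poisson | Negative binomial |
|---|---|---|---|
| 25% at 7, rest 0–3 | 2.30 | 19.8% | 7.3% |
| Constant relapse, 25% at 7 | 2.04 | 16.9% | 5.7% |
| 50% at 7, rest 0–3 | 1.93 | 15.9% | 5.6% |
| Beta-binomial, mean 4.5, ρ 0.7 | 1.86 | 15.4% | 3.9% |
| 25% at 7, rest 0–6 | 1.50 | 11.0% | 5.9% |
| Beta-binomial, mean 4.5, ρ 0.5 | 1.43 | 10.4% | 5.4% |
| Constant relapse, 50% at 7 | 1.41 | 10.2% | 5.4% |
| 50% at 7, rest 0–6 | 1.20 | 7.4% | 5.1% |
| 25% at 7, rest 1–6 | 1.02 | 5.2% | 5.0% |
| Beta-binomial, mean 5.25, ρ 0.5 | 1.00 | 5.2% | 4.0% |
| 50% at 7, rest 1–6 | 0.86 | 3.7% | 3.3% |
| Beta-binomial, mean 5.25, ρ 0.3 | 0.70 | 2.2% | 2.1% |
| Beta-binomial, mean 5.25, ρ 0.2 | 0.55 | 1.0% | 1.0% |

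Null coverage of the 95% interval is 100% minus the rate shown. Across the same rows the t-test stayed at about 5%, Poisson with Pearson-scaled errors and a t reference at 3–5%, and a dispersion-scaled binomial for days out of 7 within 2.6–4.3%. The Wilcoxon test stayed within 4.2–4.6%, so leaving t-test versus Wilcoxon open costs little.

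**Step 5: one invented dataset, to show the mechanism.** Active: 7, 7, 7, 7, 7, 3, 1, 0, 0, 0 (total 39). Sham: 7, 7, 2, 1 and six zeros (total 17). Plain Poisson: ratio 39/17 = 2.29, SE of the log ratio √(1/39 + 1/17) = 0.291, 95% CI 1.30 to 4.06, p = 0.004. The t-test on the same 20 values: difference 2.2 days, 95% CI −0.75 to 5.15, p = 0.13. Negative binomial: p = 0.22.

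**The case against.** The large error rates need one branch used naively. Section 12.1 already names negative binomial as the alternative, and that never exceeded 7.3% here. A routine rule, inflating the Poisson standard error only when the Pearson chi-square per degree of freedom exceeds 1, kept false positives at or below 6.1%. This stands as a limit on the harm. It does not close the gap, because the plan requires neither the switch nor the check, and neither addresses variance below the mean.

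The extremes rest on chosen shapes. The 19.8% row has nobody with 4, 5 or 6 days, and nothing in the documents supports that; nine of the 13 rows are at about 11% or lower. This also stands: the range illustrates what can happen and does not predict it.

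One could read 12.1 as estimation and 12.2 as testing. The documents do not say so, and 12.2 introduces its own methods as the way to obtain the secondary estimates.

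A reader might infer that a count model is simply wrong for a bounded outcome. The check does not support that: with Pearson-scaled errors the Poisson model holds its error rate. The defect is the missing ranking and the unstated standard error.

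**Conclusion.** The conflict between 12.1 and 12.2 is plain on the page and depends on no assumption. As written, the plan permits an unscaled Poisson interval. Given 10 per arm, no treatment effect and 25–50% abstinent all week, its false-positive rate runs from about 1% to 20%, with about 17% and 10% under constant daily relapse.

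Two stronger readings are not supported. A reader might infer that the reported interval will be too narrow; the documents give no distribution of abstinent days, so neither the direction nor the size of any error is known. A reader might also infer from the study calendar, which lists "Primary Outcome – number of abstinence days", that the trial's main result is affected. Sections 1.1 and 4.1 both make feasibility primary, section 4.2 places abstinent days among the secondary endpoints, and no sample-size calculation or go/no-go rule uses this interval.

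This should be fixed, but its weight is that of a secondary estimate in a 20-patient pilot.

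**What to change.** In sections 12.1 and 12.2, name one main analysis of total smoke-free days whose variance is estimated from the data. For example: the active-minus-sham difference in mean smoke-free days (0–7), with a t-based 95% confidence interval. A Poisson model, or a binomial model for days out of 7, is equally acceptable with Pearson-scaled standard errors and a t reference. State whether the 12.2 covariates apply to the chosen analysis. Label the other listed methods as sensitivity analyses, and state that unscaled model-based Poisson standard errors will not be used. State the role of maximum consecutive days; which role is for the sponsor to decide. Make the change before unblinding, so that results cannot steer the choice.

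The cost is SAP wording; the t-test is already in 12.2. If the mean difference is chosen, the effect is in days rather than a rate ratio, and the 7-day cap is not modelled.

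The center covariate at a single site (section 7.0) and the section 10.4 wording that compares an active week with a sham week in a parallel-group design are editorial. They can be tidied at the same time but carry no weight here.

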12.2 Data analysis

General considerations: All data will be analyzed in consultation ([name]) with the electronic system called REDCap (Research Electronic Data Capture). Statistical analyses will be performed using SPSS 22.0 (IBM Inc.). Baseline demographic and baseline characteristics, together with safety analyses will be performed on all enrolled subjects. Baseline values are defined as the measures on screening visit. The standard summary statistics for continuous variables are: mean, standard deviation, median, minimum and maximum. The standard summary statistics for categorical variables are: count and percentage. All statistical tests will be two-sided. For comparison of means (continuous variables), the two-sample t-test or the Wilcoxon rank sum test will be used as appropriate. For comparison of proportions (discrete data), the Chi-squared test will be used as appropriate. All test performed at significance $\alpha = 0.05$.

To assess a feasibility of the rTMS for smoking cessation in cancer patients: The numbers of subjects who were randomized and who entered and completed each visit of the study will be provided, as well as the reasons for all post-randomization discontinuations, grouped by treatment and by major reason. The discontinued subjects, protocol deviations, and subjects excluded will be provided as well.

To obtain the secondary estimates: The abstinence days, and cigarette consumption and cue-elicited craving will be compared between the active TMS and sham groups with a t-test or a repeated measures analysis of covariance model. Baseline daily number of cigarettes smoked, sex and center will be used as covariates.

To analyze the exploratory measures: cue-induced craving (QSU – Brief) and visual analog scale for craving will be measured pre and post each rTMS session. Other assessment, Carbon Monoxide, FTND, and MNWS-R will be compared between two groups.

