1.2 Secondary objectives

To obtain preliminary estimates of whether one-week active rTMS of left DLPFC tends to be more efficacious than sham rTMS during a 7-days of quit attempt laboratory model period increasing abstinence days, and also decreasing cigarette consumption and cue-elicited craving in cancer patients with smoking.

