4.3. Exploratory endpoints

Self-reported_number of cigarettes smoked per day, cue-induced craving (QSU – Brief), visual analog scale for craving and side effect will be measured pre and post each rTMS session. Other assessment, Carbon Monoxide, FTND, and MNWS-R will be completed at baseline and the last TMS. Quitting attempt will verify daily CO < 5 ppm. FTND, Feasibility metrics will also be tracked, including numbers of complete TMS sessions and dropout rate.

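### Baseline is fixed at screening, so the later pre-treatment readings at TMS 1 cannot be the baseline covariate and nothing keeps them out of the cigarette and craving outcome models

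*Combined protocol and SAP*

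**What the plan says.** - **Baseline.** Section 12.2: "Baseline values are defined as the measures on screening visit". The same section names baseline daily cigarettes, sex and center as covariates. It names no baseline craving covariate.
- **Calendar (10.5).** Baseline and TMS 1 are separate columns. The row "Secondary Outcome – cigarette per day" is marked at Baseline and at each of TMS 1 to TMS 5.
- **Start of the quit attempt (10.4).** "Participants will be asked to start a quit attempt after the first TMS session".
- **Craving (4.3).** "visual analog scale for craving and side effect will be measured pre and post each rTMS session".
- **Diary (10.2).** "This is a daily diary of all tobacco products consumed in the period between visits"; it is collected at each visit.
- **Window.** Section 1.2 asks about efficacy "during a 7-days of quit attempt laboratory model period increasing abstinence days, and also decreasing cigarette consumption and cue-elicited craving". In 12.1 the abstinence model covers "numbers of days abstinent from cigarette smoking during their 7-days following their quit attempt".
- **Cigarette and craving models.** Section 12.1 gives a mixed model for cigarettes per day. Section 12.2 gives a t-test or a repeated-measures ANCOVA for abstinence days, cigarettes and craving. Neither lists the readings that are responses, a window for cigarettes or craving, or a treatment-by-time term.

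**The concern.** The last readings before treatment are usually the most useful baseline, and this trial collects them. The plan fixes baseline at an earlier visit, however, and leaves the TMS 1 pre-session readings without a role. They are not baseline, and they are not excluded from the outcome. An analyst who follows the text could feed all five session visits into the repeated-measures model and still be within the plan.

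Two things are at stake. First, the arms are not expected to differ at a reading taken before stimulation, so averaging it with later readings pulls the estimated rTMS effect towards zero. Aim 2 exists to supply preliminary estimates of that effect. Second, pre-treatment values already in hand are not used to reduce residual variance, which is costly with 20 patients.

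**Working it through.** The documents give no effect size, SD or power calculation, so there is no stated figure to reproduce.

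**Step 1: which TMS 1 readings are untreated.**
- Cigarettes per day at TMS 1: if taken from the diary collected at that visit (10.2), the entry covers only the time since screening. It is wholly untreated and before the quit attempt.
- Craving before the TMS 1 session: untreated.
- Craving after the TMS 1 session: follows stimulation, so it is an on-treatment reading.

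**Step 2: which of these the plan assigns.** The rule in 12.2 keeps both untreated readings out of baseline. Sections 12.1 and 12.2 do not exclude them from the cigarette or craving models. For abstinence days, 12.1 does state the window, so the gap does not arise there.

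**Step 3: dilution if they are included.** Let the true arm difference be Δ at every treated reading and 0 at the untreated one. With balanced data and equal correlation between readings, a single treatment term is the arm difference in simple means over the m readings. With k untreated, it keeps (m − k)/m.
- Cigarettes, TMS 1 to 5: (0 + 4Δ)/5 = 0.80Δ.
- Craving, pre and post at five sessions: (0 + 9Δ)/10 = 0.90Δ.
- Craving, pre-session readings only: (0 + 4Δ)/5 = 0.80Δ.
- Cigarettes, responses limited to the quit attempt: 4Δ/4 = Δ. Visit-specific contrasts from TMS 2 onward also estimate Δ.

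**Step 4: what this could mean for power (illustration).** Assumed: 10 per arm (the allocation ratio is not stated), an effect of 1.0 single-reading SD, equal correlation ρ between readings, and a normal approximation, which is optimistic at this size. Two-sided alpha of 0.05 is from 12.2. For an unadjusted comparison of means over m readings:

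SD of the mean s = √(ρ + (1 − ρ)/m); power = Φ(δ / (s√(2/10)) − 1.96).

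At ρ = 0.5:
- TMS 1 included: m = 5, δ = 0.8, s = √0.60 = 0.775; 0.8/(0.775 × 0.447) = 2.31; power Φ(0.35) = 64%.
- TMS 1 excluded: m = 4, δ = 1.0, s = √0.625 = 0.791; 1/(0.791 × 0.447) = 2.83; power Φ(0.87) = 81%.

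| ρ | TMS 1 included | TMS 1 excluded |
|---|---|---|
| 0.3 | 77% | 90% |
| 0.5 | 64% | 81% |
| 0.7 | 54% | 72% |
| 0.9 | 46% | 64% |

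**Step 5: gain from the unused baseline (illustration).** With b pre-treatment readings averaged as the covariate, the residual variance is ρ + (1 − ρ)/m − ρ²/(ρ + (1 − ρ)/b). At ρ = 0.5 and m = 4:
- b = 1: 0.625 − 0.25/1 = 0.375.
- b = 2: 0.625 − 0.25/0.75 = 0.292.

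A second pre-treatment reading therefore removes (0.375 − 0.292)/0.375 = 22% of the residual variance under these assumptions.

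**The case against.** The best defence is that the plan, read as a whole, already points to the right window. Section 1.2 places abstinence, cigarettes and craving inside the 7-day attempt. Section 10.4 starts the attempt after the first session and compares arms by treatment week. Section 4.2 confines smoke-free days to the attempt. A calendar mark shows collection, not analysis: the outcome rows are also marked under Baseline, so a mark cannot mean that a reading is modelled as a response. Section 12.1 also plans displays over time, and 12.2 allows a simple t-test. A screening baseline is in itself a legitimate prespecified choice.

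Most of this stands, and it limits the point. A reader might infer any of the following, and the documents support none of them:
- *That the untreated readings do count as on-treatment outcome.* No section says so. The plan is silent for cigarettes and craving.
- *That all craving at TMS 1 precedes stimulation.* Craving is also taken after the session.
- *That every diary day between screening and TMS 1 enters the outcome, with a much larger dilution.* This runs against 1.2 and 10.4, and the length of that interval is not given.
- *That abstinence days are diluted or capped by the baseline rule.* Their window is stated. Whether the day of TMS 1 counts as a calendar day is a separate question, and it would affect both arms alike.
- *That cutting down before TMS 1 biases the comparison.* It precedes stimulation and is expected equally in both randomized, blinded arms.

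The defence does not close the gap. The cigarette model and the ANCOVA still state no window, and the baseline rule still shuts out the later pre-treatment values.

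**Conclusion.** The point holds as a gap in specification with a concrete and better alternative. The plan collects pre-treatment cigarette and craving readings at TMS 1, bars them from baseline, and does not say that they stay out of the outcome.

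The size is conditional. The arm difference keeps 80% of its value for cigarettes, or 90% for pre and post craving, only if the untreated reading is a response, the effect is averaged over all session visits, and the effect is constant after TMS 1. Otherwise the dilution is zero. The cigarette figure also assumes that the TMS 1 entry reflects smoking before the session. The documents do not state its source, and 10.5 marks the diary only at Baseline although 10.2 has it collected at each visit. The power and variance figures rest on assumed inputs and show direction and rough scale only.

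No feasibility endpoint is affected. This is worth correcting, at modest severity.

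**What to change.** In 12.2, replace the single baseline rule for these two measures:
- Baseline cigarettes per day is the diary mean from the screening visit up to TMS 1.
- Baseline craving is the pre-session value at TMS 1.
- Screening values are used only where these are missing.
- Each is the covariate in the model for its own outcome.

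In 12.1 and 12.2, state that responses for cigarettes and craving start after the TMS 1 session: the post-session TMS 1 score for craving, and the diary from TMS 1 onward for cigarettes. In 10.5, label the TMS 1 pre-session entries as baseline, and reconcile the diary row with 10.2.

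The cost is a few lines of wording, with no new data, visits or procedures. The model has one fewer post-baseline reading, and the craving model gains one covariate.
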